## **1. BACKGROUND**

### **1.1 Importance of nonalcoholic fatty liver disease**

Nonalcoholic fatty liver disease (NAFLD) is currently the most common chronic liver disease worldwide. In Hong Kong, NAFLD affects 27% of the local adult population [1], and the annual incidence is 3.4% [2]. Nonalcoholic steatohepatitis (NASH), the more active form of NAFLD with hepatic necroinflammation and accelerated fibrosis, has already become the second leading indication for liver transplantation and the third leading cause of liver cancer in the United States [3]. On the other hand, NAFLD is largely asymptomatic. Compared with other chronic liver diseases, patients with liver cancer from NAFLD/NASH often present at a late stage when curative treatment cannot be offered [4]. Besides, several drugs have now entered phase 3 development for fibrotic NASH [5]. If successful, the first NASH drugs are expected to be available at the clinic in 1 to 2 years. Therefore, it is important to identify patients with advanced NAFLD for future treatment and liver cancer surveillance.

### **1.2 High risk of severe NAFLD in patients with type 2 diabetes**

NAFLD is strongly associated with metabolic syndrome and insulin resistance. In particular, NAFLD is present in more than 50% of patients with type 2 diabetes [6]. Diabetes is also associated with the histological severity of NAFLD [7]. In a study of 6508 NAFLD patients from Japan, diabetes was associated with a 3-fold increase in the risk of liver cancer [8]. Recently, our group conducted a screening study in 1918 patients with type 2 diabetes using transient elastography (FibroScan) and showed that 18% had increased liver stiffness suspicious of advanced liver fibrosis (i.e. bridging fibrosis [F3] or cirrhosis [F4]) [9]. All these suggest that patients with type 2 diabetes represent a high-risk group worthy of case identification. However, there has been no agreed policy on how to identify patients with advanced liver disease.

### **1.3 Non-invasive prediction of advanced fibrosis by prediction scores**

The severity of liver fibrosis is a key determinant of liver-related morbidity and mortality in NAFLD patients. In a meta-analysis of 1495 biopsy-proven NAFLD patients from 5 studies, the incidence of all-cause mortality was increased by 3.5-fold and 6.4-fold in patients with bridging fibrosis (F3) and cirrhosis (F4), respectively, compared with those without fibrosis [10]. It is therefore important to identify patients with advanced fibrosis for further monitoring and management. Although we demonstrated the role of transient elastography screening in patients with type 2 diabetes [9], the number of diabetic patients exceeds the capacity of most medical centers. Besides, since diabetic patients can develop many other complications, it is important to keep the diagnostic and referral process simple.

Using liver histology as the reference standard, various groups have derived and validated

simple scores to predict advanced liver fibrosis [11]. These scores are calculated from routine clinical and laboratory parameters and have high applicability in different clinical settings. Although the scores are not as accurate as transient elastography or magnetic resonance elastography, they have high negative predictive values in excluding advanced fibrosis and are well suited for initial assessment [12, 13]. In our own study, the area under the receiver-operating characteristics curve for detecting advanced fibrosis (F3-4) and cirrhosis (F4) was 0.74 and 0.75 for the aspartate aminotransferase-to-platelet ratio index (APRI), 0.80 and 0.81 for the Fibrosis-4 (FIB-4) index, and 0.75 and 0.80 for the NAFLD fibrosis score, respectively [13]. Importantly, patients with low fibrosis scores have very low risk of developing liver-related morbidity and mortality during long-term follow-up [14, 15].

Among the published simple scores, the FIB-4 index and NAFLD fibrosis score have been consistently shown to be the most accurate in detecting advanced fibrosis by our group and others [12, 13]. We select the FIB-4 index and APRI as initial assessment in this study because we found that the NAFLD fibrosis score is increased in the majority of diabetic patients and is indiscriminating in this population (please see section on Preliminary Data for details).

#### **1.4 Care model based on fibrosis scores**

To facilitate efficient use of medical resource and identification of NAFLD patients at risk of future liver-related complications, we envision that the care model should be simple and convenient. Our center first promoted a care model to provide structured complications screening for patients with type 2 diabetes in the 1980s. At the diabetes center, patients undergo clinical assessment and laboratory tests to detect microvascular and macrovascular complications and check if they meet metabolic treatment targets. The care model has now extended to other hospitals in Hong Kong as well as other countries [16].

Since the calculation of liver fibrosis scores only require routine clinical and biochemical parameters, it would be easy to add them as one of the assessments for diabetic patients. We therefore propose including the fibrosis scores in diabetes complication screening and using electronic reminder message to suggest physicians to refer patients with elevated fibrosis scores for specialist care or further assessments. In the era of electronic health records, automatic reminder messages can improve identification of patients for appropriate screening and management [17].

## **2. AIMS**

We aim to test the hypothesis that the use of simple fibrosis scores as part of a diabetes complications screening program followed by electronic reminder messages is more effective

than usual care in prompting physicians to correctly identify patients with suspected NAFLD and advanced liver fibrosis for specialist referral or further liver assessment. Our secondary aim is to test the hypothesis that the use of fibrosis scores and electronic reminder messages can increase the number of patients with confirmed diagnosis of advanced liver fibrosis.

### **3. STUDY DESIGN OVERVIEW**

This will be a parallel group, randomized controlled trial (Figure 1). Patients fulfilling the inclusion and exclusion criteria above will be randomized 1:1 to two groups. Randomization will be carried out through the use of computer-generated list of random numbers in variable blocks of 4 to 10. Concealment of group allocation will be achieved through putting the group allocation cards in consecutively-numbered and sealed envelopes. The patients and physicians will know that the patients are in the intervention group if they see the reminder messages. When they do not see a reminder message, there will not be a specific indicator of whether the patient is in the control group or in the intervention group but having low fibrosis scores. Furthermore, the outcome assessors will be blinded to the group assignment.

For patients in the intervention group, we will calculate the fibrosis scores. For patients with increased fibrosis scores, we will type the following pop-up message in our electronic clinical management system:

*“This patient has high Fibrosis-4 index (and/or AST-to-platelet ratio index) of xxx suggestive of significant liver fibrosis. Please consider referring the patient to the hepatology clinic or arranging further test such as FibroScan.”*

The reminder message will pop up when physicians see the patient at the clinic and use the electronic clinical management system. The message will remain active for one year. Although the message is entered manually at this stage, the arrangement mimics an automated computer system. If the study results are positive, the next step is to modify the system to automate the process.

Patients in the control group will undergo the same assessments as patients in the intervention group. Although physicians will have access to the raw liver biochemistry results and platelet count, the fibrosis score results will not be specifically shown, and there will be no electronic reminder messages regardless of the fibrosis scores. This is to mimic usual care when there is no dedicated care model for case identification.

## **4. PATIENTS**

We will recruit consecutive subjects from the Diabetes Mellitus and Endocrine Centre, Prince of Wales Hospital when they attend for diabetes complications screening.

### **4.1 Inclusion criteria**

All subjects should fulfill all of the following:

- Age 18-70 years
- Having type 2 diabetes
- Provided informed written consent

### **4.2 Exclusion criteria**

Subjects having any of the following will be excluded from the study:

- Type 1 diabetes
- Already receiving specialist care by gastroenterologists or hepatologists
- Current or past history of hepatocellular carcinoma or liver decompensation
- Active malignancies other than hepatocellular carcinoma, unless in complete remission for more than 5 years

Notably, although our primary focus is to identify patients with NAFLD and advanced liver fibrosis, we will not exclude patients with other chronic liver diseases such as chronic viral hepatitis or alcohol-related liver disease. In real life, although NAFLD is the most common chronic liver disease among diabetic patients, they can also have other liver diseases. It would also be meaningful to detect those diseases, especially if advanced fibrosis has already developed.

## **5. STUDY ASSESSMENTS**

### **5.1 Clinical assessments**

At study inclusion, all patients will undergo the following assessments:

- Record medical history including past medical history and drug history
- Record smoking and alcohol consumption using a standard questionnaire
- Measure blood pressure, body weight, body height and waist circumference; body mass index is calculated as body weight (kg) divided by body height (m) squared
- Blood tests including liver biochemistry (including alanine aminotransferase [ALT], aspartate aminotransferase [AST] and gamma-glutamyl transpeptidase [GGT]), renal function test, fasting plasma glucose, hemoglobin A1c and lipids
- Standard assessment for diabetic complications including spot urine for albumin-to-

creatinine ratio for albuminuria, retinal photography for retinopathy, foot examination including monofilament and tuning fork test for peripheral neuropathy

## **5.2 Fibrosis score**

In this study, we will calculate the FIB-4 index using the following formula: age x AST (U/l) / platelet count (x109/l) /  $\sqrt{\text{ALT (U/l)}}$  [18]. APRI is calculated as AST (/upper limit of normal) / platelet count (x109/l) x 100 [19]. Table 1 lists the cutoffs for the interpretation of the fibrosis scores, with age-specific adjustments for the FIB-4 index and NAFLD fibrosis score [20].

## **5.3 Diagnostic workup at the hepatology clinic**

Regardless of group assignment and fibrosis score results, diabetic patients referred to the hepatology clinic in this project will be seen within 12 weeks. We will perform history taking and physical examination to identify risk factors of chronic liver diseases. Viral hepatitis serology will be performed if not already done. The patients will then undergo transient elastography (FibroScan, Echosens, Paris, France) for liver stiffness measurement. Transient elastography will be performed by experienced operators under the training and instructions of the manufacturer [13]. The median of 10 liver stiffness measurements will be used to reflect the severity of liver fibrosis. Our center is equipped with the M probe and XL probe to cater for patients with different body built [21]; we will follow the machine's automatic probe selection tool. We will discuss the option of liver biopsy with patients whose diagnosis is uncertain or liver stiffness is >10 kPa suspicious of advanced fibrosis [22].

# **6. DATA ANALYSIS**

## **6.1 Primary outcome**

The primary outcome is the proportion of patients with high fibrosis scores who are referred for specialist care or further liver assessments within 1 year of the baseline visit. In this study, appropriate further liver assessments for advanced liver disease include transient elastography (FibroScan), shear wave elastography, acoustic radiation force impulse, magnetic resonance elastography, liver biopsy, and specific blood biomarkers of liver fibrosis such as FibroTest and FibroMeter. This primary outcome will address our primary aim to evaluate whether a care model comprising fibrosis score testing and electronic reminder messages can increase case identification and improve the diagnostic process.

## **6.2 Secondary outcomes**

The following secondary outcomes will be analyzed:

- The proportion of patients referred for specialist care or further liver assessments, regardless of fibrosis score results.

- The proportion of patients with low fibrosis scores who are referred for specialist care. Because NAFLD is highly prevalent and only a minority of patients have advanced fibrosis, referral of patients who will unlikely develop liver-related complications to specialists represents inefficient use of precious healthcare resource and should be minimized. This notion has major resource implications, and the current study will provide important information to guide healthcare policy. We recognize that physicians may have other reasons to refer patients for specialist care (e.g. newly diagnosed viral hepatitis). The reasons for referral will be recorded and reported.
- The proportion of patients confirmed to have advanced fibrosis. In this study, a patient is considered to have confirmed advanced fibrosis if (1) liver stiffness measurement by transient elastography is >15 kPa [22], (2) a liver biopsy shows bridging fibrosis (F3) or cirrhosis (F4), (3) unequivocal radiological features of cirrhosis (cirrhosis with nodular appearance, splenomegaly, ascites or varices), or (4) clinical, radiological or endoscopic evidence of portal hypertension. In case of discrepant results, liver biopsy and unequivocal evidence of cirrhosis and/or portal hypertension will override the liver stiffness measurement results.

### **6.3 Outcome ascertainment**

Two researchers will review the clinical records of all patients for evidence of specialist referral or arrangement of further liver assessments. They will also use the electronic clinical management system to look for new specialist clinic appointments and radiological test arrangements. The researchers will be blinded to the group assignment. In case of discrepant interpretation, a third assessor will study the case and discuss with the other two assessors to come up with a consensus on whether a patient has specialist referral, further liver assessments, and advanced fibrosis.

### **6.4 Statistical analysis**

We will perform intention-to-treat analysis for all primary and secondary outcomes. All randomized patients will be analyzed for the outcomes. Patients who are lost to follow-up will be considered not to have specialist referral, further liver assessments, and confirmed advanced fibrosis. Statistical significance is taken as a two-sided p value of <0.05.

#### ***Primary outcome***

The primary outcome includes patients with high fibrosis scores in both groups and is calculated as the number of patients with specialist referral or further liver assessments divided by the total number of patients. The proportions in the two study groups will be compared by chi-square test.

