### ***Secondary outcomes***

The following secondary outcomes will all be compared by chi-square test.

- The proportion of patients with specialist referral or further liver assessments, regardless of fibrosis score results, is calculated as the number of patients with specialist referral or further liver assessments divided by the total number of patients.
- Among patients with low fibrosis scores, the proportion of patients with inappropriate specialist referrals is calculated as the number of patients referred for specialist care divided by the total number of patients.
- The proportion of patients with confirmed advanced fibrosis is calculated as the number of patients with confirmed advanced fibrosis divided by the total number of patients.

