### **6.5 Sample size calculation**

According to our preliminary data (see below), 33% of patients with type 2 diabetes had increased FIB-4 index suspicious of advanced fibrosis, and 10% had increased APRI suspicious of significant fibrosis. In our previous screening study using transient elastography, only around 10% of diabetic patients with advanced liver fibrosis were under specialist care [9]. To be conservative, we assume that 20% of patients with high fibrosis scores in the control group will be referred for specialist care or further liver assessments. We also decide that the care model would be clinically meaningful if it can at least increase the referral rate to 37% in the intervention group. To detect this difference at a 5% significance level and 80% power, we need 107 patients with high fibrosis scores per group. Using a more conservative estimation of 25% of patients having increased fibrosis scores, a total of 856 patients is needed for this study. Assuming a dropout rate of 10%, the final sample size is 952 patients (476 per arm). The assumption on dropout rate is realistic as all patients should have been on regular follow-up and we will only be observing the referral pattern and linkage to care in 1 year.

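### Cheap improvement (minor): the primary chi-square test is valid, but the comparison adjusts for no baseline value and no between-arm effect estimate with a confidence interval is planned

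*Combined protocol and SAP*

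**What the plan says.** Section 6.1 defines the endpoint: "The primary outcome is the proportion of patients with high fibrosis scores who are referred for specialist care", or for further liver assessment, within one year. Section 6.4 restricts the primary comparison to patients with high scores in both arms and states: "The proportions in the two study groups will be compared by chi-square test". For the rest: "The following secondary outcomes will all be compared by chi-square test". The decision rule is: "Statistical significance is taken as a two-sided p value of <0.05". Section 6.4 also sets intention-to-treat and counts patients lost to follow-up as having no event.

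No covariate, adjusted model, risk difference, risk ratio, odds ratio or confidence interval is named there or elsewhere. The proportion in each arm is planned; a comparison of the two with its uncertainty is not.

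The sample size in section 6.5 rests on 20% v 37% referred: "To detect this difference at a 5% significance level and 80% power, we need 107 patients with high fibrosis scores per group".

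The baseline data come from sections 3, 5.1 and 5.2. ALT and AST are measured at inclusion, and control patients have the same assessments. FIB-4 is computed from age, AST, ALT and platelets, and APRI from AST and platelets. Randomization is 1:1 in variable blocks, with no stratification factor stated.

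**The concern.** A patient enters the primary analysis only after the score has been computed, so log FIB-4 and log ALT should be almost complete there. In the preliminary data (section 6.6), 599 of 612 patients had the laboratory values needed; the other 13 (2.1%) could not have been classified.

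These values could plausibly predict referral. Control-arm physicians can see the liver tests and platelets. Intervention-arm physicians see a message that displays the score: "This patient has high Fibrosis-4 index (and/or AST-to-platelet ratio index) of xxx suggestive of significant liver fibrosis". If prediction is real, an unadjusted comparison gives up some precision that is already paid for, and the randomization does not recover it by stratification.

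The second gap needs no assumption about prediction. The purpose is to learn how much the care model raises referral. A p value alone does not show how large or small the increase could be.

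**Working it through.** **1. The plan's own figure.** Inputs from sections 6.4 and 6.5: p1 = 0.20, p2 = 0.37, two-sided 5%, 80% power, 1:1. The unpooled-variance formula is n = (1.960 + 0.842)² × [p1(1-p1) + p2(1-p2)] / (p2-p1)². This is 7.849 × (0.1600 + 0.2331) / 0.0289 = 106.8, so 107 per group. Then 2 × 107 / 0.25 = 856, and 856 / 0.90 gives 952 after rounding up. All reproduce. The pooled formula gives 110, and with a continuity correction 121. The stated 107 therefore implies the uncorrected test. Power at 107 per group is 79.1% by the pooled normal approximation.

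**2. What an interval would show.** At 20% v 37%, the standard error is √(0.3931/107) = 0.0606. The 95% CI is 17.0 ± 11.9, or 5.1 to 28.9 points.

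**3. Rough gain from adjustment.** Multiply the variance by (1 - R²). The documents give no R² for referral, so it is assumed. Power is 79.1% at R² = 0, 79.9% at 0.02, 81.1% at 0.05 and 83.2% at 0.10.

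**4. Simulation of the proposed method.** Setting: 107 per group, 20% v 37%, logistic model on arm and two covariates, standardised risk difference, leverage-corrected robust standard error, and t critical value on 214 - 4 = 210 degrees of freedom. Slopes are assumed log odds per SD on each covariate. Correlation is 0.4 unless stated. Entries are power (%), chi-square / adjusted.

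| Assumed prediction of referral | slope 0.5 | slope 0.8 |
|---|---|---|
| Controls only | 79.6 / 79.7 | 79.4 / 80.5 |
| Controls only, one covariate predictive | 79.9 / 79.1 | 80.0 / 79.5 |
| Both arms, one covariate predictive | 79.2 / 80.0 | 80.0 / 82.8 |
| Both arms, score range restricted | 80.1 / 81.2 | 79.5 / 84.0 |
| As above, half slope in intervention arm | 78.5 / 79.4 | not run |
| Both arms, correlation -0.3 | 78.7 / 80.8 | 78.2 / 82.8 |
| Both arms, full range | 79.4 / 83.1 | 79.6 / 87.8 |

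With no prediction the result is 79.1 / 78.2. The restricted-range and correlation -0.3 rows use 4,000 trials (Monte Carlo SE about 0.6 points), the others 10,000 (about 0.4). A repeat run gave 78.9 / 81.0 and 79.6 / 84.0 for the restricted range, 78.6 / 79.6 with the half slope, and 80.1 / 81.5 at correlation -0.3 with slope 0.5.

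The restricted rows are the more relevant ones. The analysis set is selected on high score. Cutting a normal covariate to its top 33% (the share with raised FIB-4 in section 6.6) leaves an SD of about 0.53, so a slope defined over all screened patients predicts less within the set. The sign of the FIB-4 and ALT correlation is also unknown, because the square root of ALT is in the denominator of FIB-4.

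**5. Validity and interval width** (10,000-trial runs). Type I error was 4.7 to 5.4% for chi-square and 4.4 to 5.2% adjusted. Coverage of the adjusted interval was 94.8 to 95.7%, and the model always converged. Mean full interval width was 23.6 points unadjusted. Adjusted, it was 24.2 with no prediction and 22.9 with slope 0.5 in both arms over the full range. About 0.20 × 107 + 0.37 × 107 = 61 events are expected, which supports two covariates.

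**6. Continuity correction.** Exact power at the design rates is 79.5% uncorrected and 74.5% corrected; exact type I error at 20% v 20% is 5.0% and 3.3%. A borderline table, 21/107 v 34/107, gives p = 0.042 and 0.060.

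**The case against.** The strongest reply is that an unadjusted comparison of two randomized proportions is a complete analysis, matches the sample size, and is simple to run and explain. The case for adjustment rests on slopes that no document supplies. Weak or control-only prediction is quite plausible: section 3 describes the control arm as usual care without a dedicated pathway, and the message gives every flagged patient the same advice. A slope of 0.8 on both covariates would imply an AUC of about 0.80 for referral in controls, which is high for such a setting. All of this stands, and it is why the expected gain is small and may be nil. It does not touch the missing effect estimate and interval.

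Four stronger readings are tempting, and the documents do not support them:

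- That the chi-square test is invalid or the trial underpowered. The set is defined by baseline values measured in the same way in both arms, type I error is about 5%, and 107 reproduces.
- That baseline values are not used at all. They define the primary analysis set; the gap is in adjustment only.
- That adjustment is free and worth about 8 points. That needs strong prediction by both covariates over an unrestricted score range, and without prediction there is a small loss.
- That the unstated continuity correction leaves the primary test open. The 107 already implies the uncorrected form, so this is a missing detail to write down.

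**Conclusion.** A minor point, and an improvement to a sound plan. The planned comparison uses no baseline covariate, and the plan contains no between-arm estimate with an interval.

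The change in power from adjustment, under assumed prognostic strength, is about -1 point with no prediction, 0 to +1 if prediction is mainly in controls, and about +1 to +4 if it holds in both arms, allowing for the restricted score range and an unknown correlation. The worst case found is about 1 point of power and an interval about 0.6 points wider (24.2 - 23.6). The restriction was approximated by truncating one normal covariate; the real set is also shaped by APRI and age-specific cut-offs.

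The benefit of reporting an interval does not depend on any of these assumptions. A reader might take the 17-point difference as a threshold that the interval must clear. Section 6.5 uses it only as the difference to detect, and the trial is not sized to exclude smaller effects.

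**What to change.** Pre-specify in section 6.4, before outcomes are compared by arm:

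- **Primary:** logistic regression of the primary outcome on arm, baseline log FIB-4 and baseline log ALT in the high-score set, reported as the standardised (marginal) risk difference with a robust, leverage-corrected 95% CI and two-sided p value. If the model does not converge, use the unadjusted risk difference. A missing covariate, which should be rare here, is set to its mean over both arms.
- **Supporting:** the chi-square test, stated to be without continuity correction, and the unadjusted risk difference with 95% CI.
- **Secondary outcomes:** keep chi-square, also uncorrected, and add the unadjusted risk difference with 95% CI.

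The marginal risk difference keeps the target on the scale of section 6.5; a conditional odds ratio would change it.

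The cost is SAP wording, one short analysis script, and up to about 1 point of power if the covariates turn out not to predict. No new data are needed, and sample size, conduct and the stated 80% power are unchanged. If the sponsor prefers to keep the unadjusted test as primary, the unadjusted risk differences with intervals and the note on continuity correction should still be added.
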